# 9.2 Data Collection

Source document and source data will be captured electronically in this trial and will meet the same fundamental elements of data quality (eg, attributable, legible, contemporaneous, original, and accurate) as paper records. These data will be collected into a system that is fully validated. Changes to the data will be captured by an automatic audit trail.

The trial site will be given a tablet to directly record subject data and clinical observations on electronic forms. Designated trial site staff will not be given access to the system until they have been appropriately trained. Information to be originally captured and reviewed electronically shall include details of the subject visit and the protocol-required assessments performed as a part of these visits, medical history, AEs, and concomitant medications. Because this trial is using an electronic source record as the original point of data capture, there is no additional data entry step for the site for data collected directly into the application - rather, the electronic source record directly populates the trial database.

Some data may be captured via paper and then entered into the eSource. These and any other data treated in this manner will be source data verified by the trial clinical research associate, and the location of the source data (ie, eSource, paper, or a local electronic system) will be documented before the trial start. Any changes to information in paper

source documents will be initialed and dated on the day the change is made by a trial site staff member authorized to make the change. Changes will be made by striking a single line through erroneous data (so as not to obliterate the original data), and clearly entering the correct data (eg, wrong data right data). If the reason for the change is not apparent, a brief explanation for the change will be written in the source documentation by the clinician.

Another exception will be safety laboratory data, where the official source documentation will be considered the report issued by the analyzing laboratory.

Remote monitoring of the original electronic source record will take place, however on-site monitoring inspections will continue to take place in order to review data entry source documentation directly captured on paper and transcribed into the system, to ensure protocol adherence, to assess site operational capabilities and to perform other monitoring activities that cannot be performed remotely.

At the end of the trial, the investigator must certify that the data entered into the eSource application are complete and accurate. After database lock, the investigator will receive an electronic copy of the subject data.

#### 9.3 File Management at the Trial Site

The investigator will ensure that the trial site file is maintained in accordance with Section 8 of the ICH GCP Guideline E6 and as required by applicable local regulations. The investigator/institution will take measures to prevent accidental or premature destruction of these documents. Per regulatory guidelines, sites must retain any documents that are uploaded to eSource.

#### 9.4 Records Retention at the Trial Site

Regulatory requirements for the archival of records for this trial necessitate that participating investigators maintain detailed clinical data for the longest of the following 3 periods:

- A period of at least 2 years after the date on which approval to market the drug is obtained (or if IMP development is discontinued, the date regulatory authorities were notified of discontinuation); OR
- A period of at least 3 years after the sponsor notifies the investigator that the final report has been filed with regulatory authorities.
- Longer, region-specific storage requirements, if applicable.

The investigator must not dispose of any records relevant to this trial without either (1) written permission from the sponsor or (2) provision of an opportunity for sponsor to collect such records. The investigator will be responsible to maintain adequate and accurate electronic or hard copy source documents of all observations and data generated during this trial including any data clarification forms received from the sponsor. Such documentation is subject to inspection by the sponsor and relevant regulatory authorities. If the investigator withdraws from the trial (eg, due to relocation or retirement), all trial-related records should be transferred to a mutually agreed-upon designee within a sponsor-specified timeframe. Notice of such transfer will be given to the sponsor in writing.

# 10 Quality Control and Quality Assurance

# 10.1 Monitoring

The sponsor has ethical, legal, and scientific obligations to follow this trial in accordance with established research principles, the ICH E6 GCP: Consolidated Guidance, and applicable regulatory requirements and local laws. As part of a concerted effort to fulfill these obligations (maintain current personal knowledge of the progress of the trial), the sponsor's monitors will visit the site during the trial, as well as communicate frequently via telephone, e-mail, and written communications. In addition, all investigators and clinical site personnel will undergo initial and ongoing training for this particular trial, and this training will be clearly documented.

#### 10.2 Auditing

The sponsor's Quality Assurance Unit (or representative) may conduct trial site audits. Audits will include, but are not limited to, IMP supply, presence of required documents, the informed consent process, and comparison of eSource with source documents. The investigator agrees to participate with audits.

Regulatory authorities may inspect the investigator site during or after the trial. The investigator will cooperate with such inspections and will contact the sponsor immediately if such an inspection occurs.

# 11 Ethics and Responsibility

This trial must be conducted in compliance with the protocol, FDA regulations, ICH GCP Guideline (E6), international ethical principles derived from the Declaration of Helsinki and Council for International Organizations of Medical Science (CIOMS) guidelines, and applicable local laws and regulations. Each trial site will seek approval/favorable opinion

by an IRB or IEC according to regional requirements, and the investigator will provide that documentation to the sponsor. The IRB/IEC will evaluate the ethical, scientific, and medical appropriateness of the trial. Further, in preparing and using screens in eSource, the investigator, subinvestigator, and their staff will take measures to ensure adequate care in protecting subject privacy. To this end, a subject number and subject identification code will be used to identify each subject.

Financial aspects, subject insurance and the publication policy for the trial will be documented in the agreement between the sponsor and the investigator.

# 12 Confidentiality

All information generated in this trial will be considered confidential and will not be disclosed to anyone not directly concerned with the trial without the sponsor's prior written permission. Subject confidentiality requirements of the region(s) where the trial is conducted will be met. However, authorized regulatory officials and sponsor personnel (or their representatives) may be allowed full access to inspect and copy the records, consistent with local requirements. All IMPs, subject bodily fluids, or other materials collected shall be used solely in accordance with this protocol, unless otherwise agreed to in writing by the sponsor.

Subjects will be identified only by unique subject numbers in eSource. If further subject identification is required, subjects' full names may be made known to a regulatory agency or other authorized officials if necessary, subject to local regulations.

# **13 Amendment Policy**

The investigator will not make any changes to this protocol without the sponsor's prior written consent and subsequent approval/favorable opinion by the IRB/IEC. Any permanent change to the protocol, whether an overall change or a change for specific trial site(s), must be handled as a protocol amendment. Any amendment will be written by the sponsor. Each amendment will be submitted to the IRB/IEC, as required by local regulations. Except for "administrative" or "non-substantial" amendments, investigators will wait for IRB/IEC approval/favorable opinion of the amended protocol before implementing the change(s). Administrative amendments are defined as having no effect on the safety of subjects, conduct or management of the trial, trial design, or the quality or safety of IMP(s) used in the trial. A protocol change intended to eliminate an apparent immediate hazard to subjects should be implemented immediately after agreement by the sponsor and investigator, followed by IRB/IEC notification within local applicable

timelines. The sponsor will submit protocol amendments to the applicable regulatory agencies within local applicable timelines.

When the IRB/IEC, investigators, or the sponsor conclude that the protocol amendment substantially alters the trial design or increases the potential risk to the subject, the currently approved written ICF will require similar modification. In such cases, after approval/favorable opinion of the new ICF by the IRB/IEC, repeat written informed consent will be obtained from subjects enrolled in the trial before expecting continued participation and before the amendment-specified changes in the trial are implemented.

# 14 Publication Authorship Requirements

Authorship for any Otsuka-sponsored publications resulting from the conduct of this trial will be based on International Committee of Medical Journal Editors (ICMJE) authorship criteria (http://www.icmje.org/recommendations). According to ICMJE guidelines, one may be considered an author only if the following criteria are met:

- 1. Substantial contributions to the conception or design of the work; or the acquisition, analysis, or interpretation of data for the work; AND
- 2. Drafting the work or revising it critically for important intellectual content; AND
- 3. Final approval of the version to be published; AND
- 4. Agreement to be accountable for all aspects of the work in ensuring that questions related to the accuracy or integrity of any part of the work are appropriately investigated and resolved.

All authors must meet the above criteria, and all who qualify for authorship based on the above criteria should be listed as authors.

Investigators or other trial participants who do not qualify for authorship may be acknowledged in publications resulting from the trial. By agreeing to participate in the trial, investigators or other trial participants consent to such acknowledgement in any publications resulting from its conduct.

# Appendix 1Criteria for Identifying Vital Signs of Potential
Clinical Relevance

| Variable                              | Criterion Value a   | Change Relative to Baseline a           |
|---------------------------------------|--|--|
| Heart Rate b               | > 120 bpm
< 50 bpm  | $\geq$ 15 bpm increase
$\geq$ 15 bpm decrease   |
| Systolic Blood Pressure b  | > 180 mmHg
< 90 mmHg  | $\geq$ 20 mmHg increase
$\geq$ 20 mmHg decrease |
| Diastolic Blood Pressure b | > 105 mmHg
< 50 mmHg  | $\geq$ 15 mmHg increase
$\geq$ 15 mmHg decrease |
| Orthostatic Hypotension               | ≥ 20 mmHg decrease in systolic blood
pressure and a ≥ 25 bpm increase in
heart rate from supine to
sitting/standing | Not Applicable
(baseline status not considered) |
| Weight                                | -  | ≥ 7% increase
≥ 7% decrease                     |

aIn order to be identified as potentially clinically relevant, an on-treatment value must meet the "Criterion Value" and also represent a change from the subject's baseline value of at least the magnitude shown in the "Change Relative to Baseline" column.

bAs defined in "Supplementary Suggestions for Preparing an Integrated Summary of Safety Information in an Original NDA Submission and for Organizing Information in Periodic Safety Updates," FDA Division of Neuropharmacological Drug Products draft (2/27/87).

| Appendix 2 | Criteria for Identifying Laboratory | Values of Potential |
|------------|--|---------------------|
|            | Clinical Relevance                         |                     |

| Laboratory Tests           | Criteria   |
|----------------------------|--|
| Chemistry                  |  |
| AST (SGOT)                 | $\geq$ 3 x ULN   |
| ALT (SGPT)                 | $\geq$ 3 × ULN   |
| Alkaline phosphatase       | $\geq$ 3 × ULN   |
| LDH                        | $\geq$ 3 × ULN   |
| BUN                        | $\geq$ 30 mg/dL  |
| Creatinine                 | $\geq$ 2.0 mg/dL   |
| Uric Acid                  |  |
| Men                        | $\geq 10.5 \text{ mg/dL}$  |
| Women                      | $\geq$ 8.5 mg/dL   |
| Bilirubin (total)          | $\geq$ 2.0 mg/dL   |
| СРК                        | $\geq$ 3 × ULN   |
| Prolactin                  | > ULN  |
| Hematology                 |  |
| Hematocrit                 |  |
| Men                        | $\leq$ 37 % and decrease of $\geq$ 3 percentage points from Baseline |
| Women                      | $\leq$ 32 % and decrease of $\geq$ 3 percentage points from Baseline |
| Hemoglobin                 |  |
| Men                        | $\leq 11.5 \text{ g/dL}$   |
| Women                      | $\leq$ 9.5 g/dL  |
| White blood count          | $\leq 2,800/$ mm  or $\geq 16,000/$ mm       |
| Eosinophils                | $\geq 10\%$  |
| Neutrophils                | $\leq 15\%$  |
| Absolute neutrophil count  | $\leq$ 1,000/ mm   |
| Platelet count             | $\leq$ 75,000/ mm  or $\geq$ 700,000/ mm     |
| Urinalysis                 |  |
| Protein                    | Increase of $\geq 2$ units   |
| Glucose                    | Increase of $\geq 2$ units   |
| Casts                      | Increase of $\geq 2$ units   |
| Additional Criteria        |  |
| Chloride                   | $\leq$ 90 mEq/L or $\geq$ 118 mEq/L                                  |
| Potassium                  | $\leq$ 2.5 mEq/L or $\geq$ 6.5 mEq/L                                 |
| Sodium                     | $\leq 126 \text{ mEq/L or} \geq 156 \text{ mEq/L}$                   |
| Calcium                    | $\leq 8.2 \text{ mg/dL} \text{ or} \geq 12 \text{ mg/dL}$            |
| Glucose                    |  |
| Fasting                    | $\geq 100 \text{ mg/dL}$   |
| Non-Fasting                | $\geq$ 200 mg/dL   |
| Total Cholesterol, Fasting | $\geq$ 240 mg/dL   |
| LDL Cholesterol, Fasting   | $\geq$ 160 mg/dL   |
| HDL Cholesterol, Fasting   |  |
| Men                        | < 40  mg/dL  |
| Women                      | < 50 mg/dL   |
| Triglycerides, Fasting     | $\geq$ 150 mg/dL   |

Confidential - Proprietary Information 95 Version 5.0, 05 Jul 2022 Until the information herein is released by Otsuka to the public domain, the contents of this document are Otsuka confidential information and should not be duplicated or re-distributed without prior written consent of Otsuka. 96

#### Appendix 3 Criteria for Identifying ECG Measurements of Potential Clinical Relevance

| Variable   | Criterion Value a  | Change Relative to Baseline a                              |
|--|---|---|
| Rate   |   |   |
| Tachycardia  | $\geq$ 120 bpm  | increase of $\geq$ 15 bpm   |
| Bradycardia  | $\leq 50 \text{ bpm}$   | decrease of $\geq$ 15 bpm   |
| Rhythm   |   |   |
| Sinus tachycardia b                       | $\geq$ 120 bpm  | increase of $\geq$ 15 bpm   |
| Sinus bradycardia c                       | $\leq$ 50 bpm   | decrease of $\geq$ 15 bpm   |
| Supraventricular premature beat                      | all   | not present $\rightarrow$ present                                     |
| Ventricular premature beat                           | all   | not present $\rightarrow$ present                                     |
| Supraventricular tachycardia                         | all   | not present $\rightarrow$ present                                     |
| Ventricular tachycardia                              | all   | not present $\rightarrow$ present                                     |
| Atrial fibrillation                                  | all   | not present $\rightarrow$ present                                     |
| Atrial flutter                                       | all   | not present $\rightarrow$ present                                     |
| Conduction   |   |   |
| 1° atrioventricular block                            | $PR \ge 200 \text{ msec}$   | increase of $\geq$ 50 msec  |
| 2° atrioventricular block                            | all   | not present $\rightarrow$ present                                     |
| 3° atrioventricular block                            | all   | not present $\rightarrow$ present                                     |
| Left bundle-branch block                             | all   | not present $\rightarrow$ present                                     |
| Right bundle-branch block                            | all   | not present $\rightarrow$ present                                     |
| Pre-excitation syndrome                              | all   | not present $\rightarrow$ present                                     |
| Other intraventricular conduction block d | $QRS \ge 120 \text{ msec}$  | increase of $\geq 20$ msec  |
| Infarction   |   |   |
| Acute or subacute                                    | all   | not present $\rightarrow$ present                                     |
| Old  | all   | not present $\rightarrow$ present
$\geq 12$ weeks post-trial entry |
| ST/T Morphological                                   |   |   |
| Myocardial Ischemia                                  | all   | not present $\rightarrow$ present                                     |
| Symmetrical T-wave inversion                         | all   | not present $\rightarrow$ present                                     |
| Increase in QTc                                      | QTcF or QTcN
$\geq$ 450 msec for males,
$\geq$ 470 msec for females |   |

aIn order to be identified as potentially clinically relevant, an on-treatment value must meet the "Criterion Value" and also represent a change from the subject's baseline value of at least the magnitude shown in the "Change Relative to Baseline" column.

bNo current diagnosis of supraventricular tachycardia, ventricular tachycardia, atrial fibrillation, atrial flutter, or other rhythm abnormality.

cNo current diagnosis of atrial fibrillation, atrial flutter, or other rhythm abnormality.

dNo current diagnosis of left bundle branch block or right bundle branch block.

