#### 7.6.4 Electrocardiogram Data

Mean change from baseline and the incidence of clinically significant changes will be calculated for ECG parameters.

For the analysis of QT and QTc, data from 3 consecutive complexes (representing 3 consecutive heart beats) will be measured to determine average values. The following QT corrections will be used for reporting purposes in the clinical study report:

- 1) QTcF is the length of the QT interval corrected for heart rate by the Fridericia formula:  $QTcF = QT/(RR)^{0.33}$
- 2) QTcN is the length of the QT interval corrected for heart rate by the FDA Neuropharm Division formula:  $QTcN = QT/(RR)^{0.37}$

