9.7 Electrocardiogram Data

ECG data will be summarized by mean change from baseline by treatment group by visit. For the analysis of QT and QTc, data from 3 consecutive complexes (representing 3 consecutive heart beats) will be measured to determine average values. The following QT corrections will be used:

- QTcF is the length of the QT interval corrected for heart rate by the Fridericia formula: QTcF=QT/(RR)^{0.33}
- 2) QTcN is the length of the QT interval corrected for heart rate by the FDA Neuropharm Division formula: QTcN=QT/(RR)^{0.37}

Incidence of potentially clinically significant treatment emergent ECG abnormalities will also be summarized by treatment groups. Criteria of potentially clinically significant ECG abnormalities are provided in Appendix 3.

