Old	all	not present \rightarrow present ≥ 12 weeks post study entry
Myocardial Ischemia	all	not present \rightarrow present
Symmetrical T-wave inversion	all	not present \rightarrow present
Increase in QTc	QTcF or QTcN \geq 450 msec for males, \geq 470 msec for	

^aIn order to be identified as potentially clinically relevant, an on-treatment value must meet the "Criterion Value" and also represent a change from the subject's baseline value of at least the magnitude shown in the "Change Relative to Baseline" column.

^bNo current diagnosis of supraventricular tachycardia, ventricular tachycardia, atrial fibrillation, atrial flutter, or other rhythm abnormality.

^cNo current diagnosis of atrial fibrillation, atrial flutter, or other rhythm abnormality.

^dNo current diagnosis of left bundle branch block or right bundle branch block.

Confidential - Proprietary Information4014 Mar 2023

Until the information herein is released by Otsuka to the public domain, the contents of this document are Otsuka confidential information and should not be duplicated or re-distributed without prior written consent of Otsuka.

This page is a manifestation of an electronically captured signature

SIGNATURE PAGE

Document Name: SAP 331-10-234

Document Number: CCI

Signed by	Meaning of Signature	Server Date (dd-MMM- yyyy hh:min) - UTC timezone
PPD	Clinical Approval	14-Mar-2023 12:44:19
PPD	Biostatistics Approval	14-Mar-2023 13:45:35

Otsuka Pharmaceutical Development & Commercialization, Inc.

Investigational New Drug Brexpiprazole (OPC-34712)

Protocol 331-10-234 IND No. 101,871 EudraCT No. 2017-001447-12

A Multicenter, Randomized, Double-blind, Placebo- and Active-controlled Trial to Evaluate the Efficacy of Brexpiprazole Monotherapy for the Treatment in Adolescents (13-17 years old) With Schizophrenia

Statistical Analysis Plan Addendum to v2.0

Version: Final Date: 21 Aug 2023

Protocol Date: 05 Jul 2022

Confidential May not be used, divulged, published or otherwise disclosed without the consent of Otsuka Pharmaceutical Development & Commercialization, Inc.

Confidential - Proprietary Information1Version Date: 21 Aug 2023Until the information herein is released by Otsuka to the public domain, the contents of this document are Otsuka
confidential information and should not be duplicated or re-distributed without prior written consent of Otsuka.

Table of Contents

Tal	ble of Contents	2
Lis	t of Abbreviations and Definitions of Terms	3
1	Introduction	4

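### The QTc row of the ECG outlier criteria tests a level rather than an increase, so rises ending below 450/470 msec are absent from the ECG incidence table; the Old infarction row cannot be met on the ECG schedule

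*Protocol*

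**What the plan says.** Protocol 7.6.4 states: "Mean change from baseline and the incidence of clinically significant changes will be calculated for ECG parameters". SAP 9.7 plans mean change by treatment group and visit, names QTcF and QTcN as the corrections, and adds: "Incidence of potentially clinically significant treatment emergent ECG abnormalities will also be summarized by treatment groups". The criteria for that incidence table are in Appendix 3.

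Footnote a of Appendix 3, the same in both documents, joins two conditions: "an on-treatment value must meet the 'Criterion Value' and also represent a change from the subject's baseline value of at least the magnitude shown". The other numerical rows carry such a change: 15 bpm for rate, 50 msec for PR, 20 msec for QRS. The row "Increase in QTc" carries only the 450/470 msec limits. Its change cell is blank in the protocol text. The SAP row breaks off before the end of the criterion, so its change cell cannot be judged.

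The same limits exclude subjects at entry (Protocol Table 3.4.3-1, criterion 16).

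The Old infarction row requires new appearance at least 12 "weeks post-trial entry" (protocol) or "12 weeks post study entry" (SAP Appendix 3). Protocol Table 3.7-1 schedules ECGs at screening, Day 1 predose and Week 6/ET. The follow-up contact has none.

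**The concern.** A row named for an increase should identify subjects whose QTc increased. This one identifies subjects whose QTc ended at or above a limit. The two differ most for subjects who start well below the limit, and the entry criterion selects subjects below it. A large individual rise that ends just under the limit leaves no trace in the incidence table, and no other categorical summary of QTc change is described in Protocol 7.6.4 or SAP 9.7. A mean change does not show how many individuals had large rises, which is the purpose of an incidence table.

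The missing magnitude is a separate fault and works in the opposite direction. With a blank cell, footnote a gives the programmer no change to apply, and a subject at the limit both at baseline and on treatment could be counted. That can occur: Protocol 3.7.3.4 says that central baseline ECG results are not available before randomization.

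The Old infarction row is a small drafting fault of another kind: a time condition longer than the period with scheduled ECGs.

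**Working it through.** **ECG calendar**

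- Plan's own figure: 28 days screening + 42 treatment + 21 follow-up = 91 days = 13.0 weeks, as stated in Protocol 3.7.
- Last scheduled ECG, counted from the start of a full 28-day screening with the +2-day visit window: (28 + 42 + 2)/7 = 72/7 = 10.3 weeks.
- Using the Day 49 upper limit of SAP Table 3.4-1: (28 + 49)/7 = 11.0 weeks. That table is written for rating scales; it is used here only as the most generous limit.
- The row needs 12 × 7 = 84 days. Screening would have to last 84 − 44 = 40 days or, without the window, 84 − 42 = 42 days. Protocol 3.7.1.1 allows an extension beyond 28 days, but the standard schedule cannot reach 84.

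**Rise needed to be flagged**

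Rise needed = limit − baseline.

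- From 390 msec: 450 − 390 = 60 (male); 470 − 390 = 80 (female).
- From 420 msec: 30 (male); 50 (female).
- Not flagged: male 390 to 449 (+59); female 390 to 469 (+79). The rule is an *and* rule, so a change value lost from the printed cell could only make the row stricter. These cases stay unflagged under either reading.

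**Share of rises missed**

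The documents give no QTc distribution, so all inputs here are assumptions. Half the subjects are male. Baseline B is normal, truncated below the limit L (450 or 470). The change D is normal and independent of B. A subject is flagged if B + D ≥ L. The share of rises above c that is missed is P(B + D < L | D > c), computed by numerical integration and averaged over the sexes.

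Base case: B mean 400, SD 18; SD of D 15; 105 subjects per arm.

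| Mean effect | Rise > 30 msec | Of these, missed | Flagged by the row |
|---|---|---|---|
| 0 | 2.3% (2.4 of 105) | 87% | 0.8% (0.9 of 105) |
| +10 | 9.1% (9.6 of 105) | 86% | 2.3% (2.5 of 105) |
| +20 | 25.2% (26.5 of 105) | 83% | 5.7% (6.0 of 105) |

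Sensitivity at +20 msec, rises above 30 msec missed:

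- B 410 (SD 20), SD of D 15: 69%. With SD of D 20: 62.5%.
- B 390 (SD 18), SD of D 20: 88%. With SD of D 15: 92.1%.

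Rises above 60 msec, base case at +20 msec: 0.38% of subjects (0.4 of 105), of which about 41% are missed.

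**Check with a fixed rise**

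Share flagged = [F(L) − F(L − rise)]/F(L), where F is the baseline distribution. With baseline 400 (SD 20) and a rise of 30:

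- Male: [Φ(2.5) − Φ(1.0)]/Φ(2.5) = (0.9938 − 0.8413)/0.9938 = 15.3%.
- Female: [Φ(3.5) − Φ(2.0)]/Φ(3.5) = (0.9998 − 0.9772)/0.9998 = 2.3%.

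Over baseline means 390 to 420 and SDs 15 to 20, a fixed +30 msec rise is flagged in 2% to 49% of males and 0% to 15% of females. A fixed +60 msec rise is flagged in 50% to 98% of males and 9% to 75% of females.

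**The case against.** The strongest reply is that a reader might infer that most QTc rises go uncounted or that the row will be close to empty, and neither follows.

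- Sub-threshold rises enter the mean change planned in Protocol 7.6.4 and SAP 9.7. In the +20 msec case the arm difference would be 20/(15 × √(2/105)) = 9.7 standard errors, so that summary would show it plainly.
- The row flags about 6 of 105 subjects at +20 msec against about 1 of 105 with no effect, so it separates the arms.
- The high share missed applies to rises above 30 msec. For rises above 60 msec it is about 41% of a very small group.
- A blank change cell does not cause misses. It makes the row more inclusive; the misses come from the absolute limit.
- An absolute limit matching the entry limit is a coherent outlier definition, and investigators review every ECG for clinical significance (Protocol 3.7.3.4).
- Protocol 1.1.2 reports QTc prolongation in dogs at 30 mg/kg and hERG inhibition, but also a finding it reads as low proarrhythmic potential.
- New acute or subacute infarction has its own row with no time condition, so the Old row loses little.

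All of this stands. It limits the point to the incidence table and to its label, and rules out any inference of harm. It does not supply a count of individual increases, or the change magnitude that footnote a calls for. The words treatment emergent in SAP 9.7 may be meant to exclude subjects already at the limit at baseline, but the SAP defines the term only for adverse events.

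**Conclusion.** The point holds in a limited form. The QTc row is a level criterion under an increase label, with no visible change magnitude, and rises ending below 450/470 msec are absent from the incidence table. This does not depend on whether the blank cell is an extraction loss. What does depend on it is the second fault, counting a subject at the limit at baseline with no rise; the source document must settle that.

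Under the assumed base case the row misses about 83% to 87% of rises above 30 msec for mean effects of 0 to +20 msec, and 62.5% to 92.1% over the alternative baselines and change SDs tried at +20 msec. These figures illustrate; the documents supply none of the inputs. The documents do not support a claim that QTc rises go unanalysed or that the table will show no cases.

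The Old infarction row is wrong as written: no scheduled ECG can meet it with a 28-day screening. Only an extended screening or an off-schedule ECG could, and footnote a restricts flags to on-treatment values. The practical effect is small.

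Overall this is a cheap improvement to safety reporting. It does not affect the primary analysis.

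**What to change.** 1. Check the QTc change cell in both appendices against the source documents and reconcile it with footnote a.
2. In Appendix 3, relabel the row as a QTc value criterion, and state that it counts only subjects whose baseline is below the limit.
3. In SAP 9.7, add a table by treatment group of change from baseline in QTcF and QTcN by category, regardless of the absolute value. More than 30 and more than 60 msec are examples; the documents name no categories, so the sponsor should fix them before unblinding.
4. For Old infarction, drop the 12-week condition or the row.

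The cost is SAP wording and one extra table from ECGs already collected.
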